11.3 Early Termination of Subjects from the Study

Subjects are free to withdraw from the study at any time for any reason.

In addition, subjects may be withdrawn from the study by the PI or designee for the following reasons:

- AEs.
- Difficulties in blood collection.
- Positive pregnancy test.
- Positive urine drug and alcohol test.

A subject may be withdrawn by the PI, designee or the Sponsor if any of these considers enrollment of the subject into the study is inappropriate, the study plan is violated, or for administrative and/or other safety reasons. Prompt notification to the Sponsor of withdrawal of any subject should be provided.

Subjects who withdraw from the study will undergo early termination procedures as outlined in the Study Events Flow Chart (Section 6) in [Table 1](#) and [Table 2](#).

11.4 Study Restrictions

11.4.1 Prohibitions and Concomitant Medication

Consumption of foods and beverages containing the following substances will be prohibited as indicated:

- Xanthines/Caffeine: 24 hours prior to the first dose and throughout the study (small amounts of caffeine derived from normal foodstuffs e.g., 250 mL/8 oz./1 cup decaffeinated coffee or other decaffeinated beverage, per day, with the exception of espresso; 45 g/1.5 oz. chocolate bar, per day, would not be considered a deviation to this restriction);
- Alcohol: 48 hours prior to the first dose and throughout the study;
- Grapefruit/Seville orange: 14 days prior to first dose and throughout the study.
- Other Fruit Juice: 72 hours prior to the first dose and throughout the study;
- Vegetables from the mustard green family (e.g., kale, broccoli, watercress, collard greens, kohlrabi, Brussels sprouts, and mustard), and charbroiled meats: 7 days prior to first dose and throughout the study.

Concomitant medications will be prohibited as listed in the exclusion criteria in [Section 11.2](#). After first dosing, acetaminophen (up to 2 g per 24 hours) may be administered at the discretion of the PI or designee.

If deviations occur, the PI or designee in consultation with the Sponsor if needed will decide on a case-by-case basis whether the subject may continue participation in the study.

All medications (including vitamins and herbal supplements) taken by subjects during the course of the study will be recorded.

Use of any tobacco- and/or nicotine-containing products will be prohibited throughout the study.

11.4.2 Meals

Water (except water provided with each dosing and meals/snacks) will be prohibited 1 hour prior to and 1 hour after each study drug administration, but will be allowed ad libitum at all other times. Other fluids may be given as part of meals and snacks but will be restricted at all other times throughout the confinement period.

Subjects will fast overnight for at least 10 hours prior to study drug administration on Day 1 (Parts 1 and 2) and Day 10 (Part 2 only) and subjects will continue the fast for at least 4 hours postdose. Meals and snacks will be provided at the appropriate times thereafter.

When the subjects are confined, standard meals and snacks will be provided at appropriate times, except when they are required to fast. When confined in the CRU, subjects will be required to fast from all food and drink except water between meals and snacks.

Each meal and/or snacks served at the CRU will be standardized and will be similar in caloric content and composition and will be taken at approximately the same time in each period.

Part 1 (Itraconazole):

For all doses in Period 2 other than on Day 1, subjects will be given a standard breakfast approximately 30 minutes prior to their scheduled morning dose. Subjects will fast for at least 2 hours following the dose.

Part 2 (Rifampin):

For all doses in Period 2 other than on Day 1 and Day 10, subjects will be required to fast for at least 1 hour prior to their scheduled morning dose and will continue to fast for at least 2 hours following the dose.

11.4.3 Activity

Subjects will remain ambulatory or seated upright for the first 4 hours postdose on Day 1 (Parts 1 and 2) and Day 10 (Part 2), except when they are supine or semi-reclined for study procedures. However, should AEs occur at any time, subjects may be placed in an appropriate position or will be permitted to lie down on their right side.

There is no specific restriction of activity after dosing on other days.

Subjects will be instructed to refrain from strenuous physical activity which could cause muscle aches or injury, including contact sports at any time from screening until completion of the study.

12 TREATMENTS

12.1 Treatments Administered

LOXO-292 will be supplied as a 20 mg or 80 mg capsules.

Itraconazole will be supplied as 100 mg capsules.

Rifampin will be supplied as 300 mg capsules.

Treatments are described as follows:

Part 1 (Itraconazole, Sentinel subjects CCI

Treatment A (Period 1): 160 mg LOXO-292 (2 x 80 mg[§] capsules) at Hour 0 on Day 1.

Treatment B (Period 2): 200 mg itraconazole (2 x 100 mg capsules) administered approximately every 24 hours from Day -4 to Day 7 (within ± 1 hour of dosing time on Day -4), with 160 mg LOXO-292 (2 x 80 mg[§] capsules) coadministered at Hour 0 on Day 1.

Part 1 (Itraconazole, Remaining subjects CCI

Treatment A (Period 1): 160 mg LOXO-292 (2 x 80 mg[§] capsules)* at Hour 0 on Day 1.

Treatment B (Period 2): 200 mg itraconazole (2 x 100 mg capsules) administered approximately every 24 hours from Day -4 to Day 7 (within ± 1 hour of dosing time on Day -4), with 160 mg LOXO-292 (2 x 80 mg[§] capsules)* coadministered at Hour 0 on Day 1.

On Day 1 of both Periods 1 and 2, study drug(s) will be administered following an overnight fast. On all other dosing days in Period 2, itraconazole will be administered approximately 30 minutes after the start of a standard breakfast. All study drugs will be administered with approximately 240 mL of water.

[§] The 2 x 80 mg capsules may be substituted for 8 x 20 mg capsules. If the study drugs cannot all be swallowed at the same time, the drug administration may be divided; however, dosing should be completed within 10 minutes. Additional water, up to a maximum of 50 mL may be administered as required by the subject.

* Following completion of the sentinel group, the PI and Sponsor will review all pertinent safety and tolerability data from the sentinel group before proceeding to dose the remaining subjects.

Part 2 (Rifampin CCI

Treatment C (Period 1): 160 mg LOXO-292 (2 x 80 mg[§] capsules) at Hour 0 on Day 1.

Treatment D (Period 2): 600 mg rifampin (2 x 300 mg capsules) administered approximately every 24 hours on Day 1 to Day 16 (within \pm 1 hour of dosing time on Day 1), with 160 mg LOXO-292 (2 x 80 mg[§] capsules) coadministered at Hour 0 on Day 1 and Day 10.

All study drugs will be administered orally under fasting conditions, with approximately 240 mL of water.

[§] The 2 x 80 mg capsules may be substituted for 8 x 20 mg capsules. If the study drugs cannot all be swallowed at the same time, the drug administration may be divided; however, dosing should be completed within 10 minutes. Additional water, up to a maximum of 50 mL may be administered as required by the subject.

Parts 1 and 2:

Subjects will be instructed not to crush, split, or chew the study drugs.

The pharmacy at the CRU will provide each dose in individual unit dose containers for each subject and for each study period.

The exact clock time of dosing will be recorded.

12.2 Dose Modification

In Part 1, the dose and administration of LOXO-292 may be reduced following review of the sentinel safety data. The dose and administration of itraconazole to any subject may not be modified.

In Part 2, the dose and administration of the study drug to any subject may not be modified.

If necessary a subject must be discontinued for the reasons described in Section 11.3.

12.3 Method of Treatment Assignment

Each subject will be assigned a unique identification number upon screening. Subjects who complete the study screening assessments and meet all the eligibility criteria will be assigned a unique identification number at the time of the first dosing, different from the screening number, and will receive the corresponding product.

Subjects will receive each treatment on one occasion. Subjects will participate in only one study part, not both.

If replacement subjects are used, the replacement subject number will be 100 more than the original (e.g., Subject No. 101 will replace Subject No. 001).

12.4 Blinding

This is an open-label study.

12.5 Treatment Compliance

A qualified designee will be responsible for monitoring the administration of the timed oral doses. A mouth check will be performed by the qualified designee to ensure that the subjects have swallowed the study drug. Once a subject has finished the dosing water, the qualified designee will use a flashlight and a tongue depressor to check the subject's mouth. Subjects' hands will also be verified to ensure that the study drug was ingested.

13 STUDY ASSESSMENTS AND PROCEDURES

The Study Events Flow Chart ([Section 6](#)) summarizes the clinical procedures to be performed at each visit. Individual clinical procedures are described in detail below. Additional evaluations/testing may be deemed necessary by the PI or designee and/or the Sponsor for reasons related to subject safety.

For this study, the blood collection for LOXO-292 is the critical parameter and needs to be collected as close to the exact time point as possible. All other procedures should be completed as close to the prescribed/scheduled time as possible, but can be performed prior or after the prescribed/scheduled time.

Any nonscheduled procedures required for urgent evaluation of safety concerns take precedence over all routine scheduled procedures.

13.1 Screening

Within 28 days prior to the first dosing, medical history and demographic data, including name, sex, age, race, ethnicity, body weight (kg), height (cm), BMI (kg/m²) and history of tobacco use will be reported. Each subject will have a physical examination, vital sign measurements (heart rate, blood pressure, temperature, and respiratory rate), 12-lead ECG, and the laboratory tests of hematological, coagulation, hepatic and renal function and additional tests as noted in [Section 13.2.5](#).

13.2 Safety Assessments

13.2.1 Physical Examination

A full physical examination or an abbreviated physical examination will be performed as outlined in the Study Events Flow Chart ([Section 6](#)).

Abbreviated physical examination will include at the minimum, examination of respiratory, cardiovascular, and gastrointestinal systems, with the option for further examination of additional systems as necessary based on reported symptoms/AEs.

Symptom-driven physical examinations may be performed at any time, if deemed necessary by the PI or designee.

13.2.2 Vital Signs

Single measurements of body temperature, respiratory rate, blood pressure, and heart rate, will be measured as outlined in the Study Events Flow Chart ([Section 6](#)). Additional vital signs may be taken at any other times, if deemed necessary.

Blood pressure, heart rate, and respiratory rate measurements will be performed with subjects in a seated position, except when they are supine or semi-reclined because of study procedures and/or AEs (e.g. nausea, dizziness) or if deemed necessary by the PI or designee.

Blood pressure, heart rate, and respiratory rate will be measured within 24 hours prior to Day 1 dosing of Period 1 and Day -4 of Period 2 in Part 1 and within 24 hours prior to Day 1 dosing of Period 1 and Period 2 in Part 2 for the predose time point. At all other predose time points, blood pressure, heart rate, and respiratory rate will be measured within 2 hours prior to dosing. When scheduled postdose, vital signs will be performed within approximately 15 minutes of the scheduled time point.

13.2.3 ECG Monitoring

Single 12-lead ECGs will be performed as outlined in the Study Events Flow Chart ([Section 6](#)). Additional ECGs may be taken at any other times, if deemed necessary by the PI or designee.

ECGs will be performed with subjects in a supine position. All ECG tracings will be reviewed by the PI or designee.

ECGs will be measured within 24 hours prior to Day 1 dosing of Period 1 and Day -4 of Period 2 in Part 1 and within 24 hours prior to Day 1 dosing of Period 1 and Period 2 in Part 2 for the predose time point. At all other predose time points, ECGs will be collected within 2 hours prior to dosing. When scheduled postdose, ECGs will be performed within approximately 20 minutes of the scheduled time point.

13.2.4 Body Weight

Body weight (kg) will be reported as outlined in the Study Events Flow Chart ([Section 6](#)).

13.2.5 Clinical Laboratory Tests

All tests listed below will be performed as outlined in the Study Events Flow Chart (Section 6). In addition, laboratory safety tests may be performed at various unscheduled time points, if deemed necessary by the PI or designee.

Hematology

- Hemoglobin
- Hematocrit
- Total and differential leukocyte count
- Red blood cell count
- Platelet count

Coagulation

- Prothrombin Time/International normalized ratio
- Activated partial thromboplastin time

Serum Chemistry*

- Blood Urea Nitrogen
- Bilirubin (total and direct)
- Alkaline phosphatase
- Aspartate aminotransferase
- Alanine aminotransferase
- Albumin
- Sodium
- Potassium
- Magnesium
- Chloride
- Glucose (fasting)
- Creatinine**
- Cholesterol
- Triglycerides
- Phosphorus
- Creatine kinase
- Amylase
- Lipase

Urinalysis

- pH
- Specific gravity
- Protein***
- Glucose
- Ketones
- Bilirubin
- Blood***
- Nitrite***
- Urobilinogen
- Leukocyte esterase***

Additional Tests

- HIV test
- HBsAg
- HCV
- Urine drug screen
 - Opiates
 - Opioids (methadone, oxycodone, and fentanyl)
 - Amphetamines
 - Barbiturates
 - Benzodiazepines
 - Cocaine
 - Cannabinoids
- Urine alcohol screen
- Serum pregnancy test (for females only)
- FSH (for postmenopausal females only)
- Thyroid stimulating hormone

* Serum chemistry tests will be performed after at least a 12-hour fast at screening (Parts 1 and 2) and at check-in; at other scheduled times, serum chemistry tests will be performed after at least an 8-hour fast. However, in case of dropouts or rechecks, subjects may not have fasted for 12 or 8 hours prior to the time that the serum chemistry sample being taken.

** At screening both study parts and on Day -1 of Period 1, Part 2, creatinine clearance will be calculated using the Cockcroft-Gault formula.

*** If urinalysis is positive for protein, blood, nitrite and/or leukocyte esterase, a microscopic examination (for red blood cells, white blood cells, bacteria, casts, and epithelial cells) will be performed.

13.2.6 Adverse Events

13.2.6.1 Adverse Event Definition

An AE means any untoward medical occurrence associated with the use of a drug in humans, whether or not considered drug related.

A suspected adverse reaction means any AE for which there is a reasonable possibility that the drug caused the AE. Reasonable possibility means there is evidence to suggest a causal relationship between the drug and the AE.

An AE can therefore be any unfavorable and unintended sign (including an abnormal laboratory finding), symptom, or disease temporally associated with the use of a medicinal (investigational) product, whether or not related to the medicinal (investigational) product.

13.2.6.2 Monitoring

Subjects will be monitored from screening (signing of informed consent) and throughout the study for adverse reactions to the study drugs and/or procedures. Prior to release, subjects will be asked how they are feeling. At the follow-up, subjects will be queried with an open-ended question such as: 'How have you been feeling since your last visit?'

AEs (whether serious or non-serious) and clinically significant abnormal laboratory test value(s) will be evaluated by the PI or designee and treated and/or followed up until the symptoms or value(s) return to normal, or acceptable levels, as judged by the PI or designee and confirmed by the Sponsor.

Treatment of serious adverse events (SAEs) will be performed by a physician, either at Celerion or at a nearby hospital emergency room. Where appropriate, medical test(s) and/or examination(s) will be performed to document resolution of event(s). Outcome may be classified as resolved, improved, unchanged, worse, fatal, or unknown (lost to follow-up).

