8.3 Risks and/or Benefits to Subjects

The dose of LOXO-292 administered in this study is not anticipated to induce any potential risk or benefit to subjects participating in this study as it is a single dose which does not exceed the highest dose safely administered in first in human studies [Investigator's Brochure 2018]. The dose of itraconazole and rifampin administered in this study is not anticipated to induce any potential risk or benefit to subjects participating in this study, as they are multiple doses administered according to the dosing recommendations [itraconazole capsules; Mylan Company Inc., rifampin capsules; Lannett Company Inc.] and have been administered safely at the current dosing regimen in previous clinical studies [Templeton al., 2011; Ke et al., 2014; Tortorici et al., 2014; and Tran et al., 1999].

The safety monitoring practices employed by this protocol (i.e., 12-lead ECG, physical examinations, vital signs, clinical laboratory tests, and AE questioning) are adequate to protect the subjects' safety. In addition, as an inhibitory effect is anticipated in Part 1 of the study and LOXO-292 exposure levels are expected to be increased when coadministered with multiple-dose itraconazole, Part 1 was planned with a sentinel group where only 3 subjects will first receive the dose of 160 mg LOXO-292 with and without itraconazole. Following

review of all pertinent safety and tolerability data, a decision will be made to either continue Part 1 for the remaining subjects and to confirm the dose.

There will be no direct health benefit for study participants from receipt of study drug. An indirect health benefit to the healthy subjects enrolled in this study is the free medical tests received at screening and during the study.

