10.1.1 Confinement, Return Visits, and Follow-Up

Part 1 (Itraconazole):

Subjects will be housed on Day -1 of Period 1, at the time indicated by the CRU until after the last PK blood draw and/or study procedures scheduled on Day 8 of Period 2 as indicated in the Study Events Flow Chart ([Section 6](#)).

Part 2 (Rifampin):

Subjects will be housed on Day -1 of Period 1, at the time indicated by the CRU, until after the last PK blood draw and/or study procedures scheduled on Day 17 of Period 2 as indicated in the Study Events Flow Chart ([Section 6](#)).

Parts 1 and 2 (see [Table 1](#) and [Table 2](#)):

Subjects are confined throughout the washout period.

At all times, a subject may be required to remain at the CRU for longer at the discretion of the PI or designee.

The CRU will contact all subjects who received at least one dose of study drug (including subjects who terminate the study early) using their standard procedures (i.e., phone call or other method of contract) approximately 7 days after the last study drug administration to determine if any AE has occurred since the last study visit.

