14.3.3 Safety Analyses

All safety data will be populated in the individual CRFs. All safety data, including dosing dates and times will be listed by subjects.

AEs will be coded using the Medical Dictionary for Regulatory Activities (MedDRA[®]) and summarized by treatment for the number of subjects reporting the treatment emergent adverse event (TEAE) and the number of TEAEs reported. A by-subject AE data listing including verbatim term, coded term, treatment, severity, and relationship to treatment will be provided.

Safety data including ECGs, physical examinations, vital signs assessments, and clinical laboratory results will be summarized by treatment and point of time of collection.

Quantitative safety data as well as the difference to baseline, when appropriate, will be summarized using the appropriate descriptive statistics.

Concomitant medications will be listed by subject and coded using the WHO drug dictionary. Medical history will be listed by subject.

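### The only adverse-event questions given a time come at release and at follow-up, both after coadministration for completers, so elicitation may be unequal between treatments

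*Protocol*

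**What the plan says.** Protocol Section 13.2.6.2 begins with general surveillance: "Subjects will be monitored from screening (signing of informed consent) and throughout the study for adverse reactions to the study drugs and/or procedures". It then gives two direct questions with a time. The first is at discharge: "Prior to release, subjects will be asked how they are feeling". The second comes later: "At the follow-up, subjects will be queried with an open-ended question", and its sample wording reaches back only to the previous visit.

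Section 10.1.1 fixes when discharge happens. Subjects enter on Day -1 of Period 1 and do not leave between periods: "Subjects are confined throughout the washout period". Part 1 subjects stay "until after the last PK blood draw and/or study procedures scheduled on Day 8 of Period 2" and Part 2 subjects "until after the last PK blood draw and/or study procedures scheduled on Day 17 of Period 2". Follow-up is about a week after the final dose of any study drug.

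Section 8.3 lists the safety practices as "12-lead ECG, physical examinations, vital signs, clinical laboratory tests, and AE questioning", with no times. Section 13.2.6.3 requires every AE after the first dose to be reported, under one rule for both periods. Section 14.3.3 has AEs "summarized by treatment for the number of subjects reporting the treatment emergent adverse event (TEAE) and the number of TEAEs reported". Section 9.1 makes the safety and tolerability of LOXO-292, alone and coadministered, the secondary objective of each part.

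**The concern.** Asking people how they feel brings out events that they would not have volunteered. If the question is put only after one treatment, that treatment can look worse in a side-by-side table even when the true rates are equal. Here every completer takes LOXO-292 alone first and coadministered second, so an imbalance in questioning runs the same way for each of them and cannot average out. It is a matter of how events are found. Dividing counts by days of observation would not remove it, and an analysis plan cannot recover events that nobody asked about.

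What is at stake is the reading of the by-treatment table that serves the secondary objective. In a study this small, one or two additional subjects with an event would be visible in it.

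**Working it through.** The protocol states no figure for this point, so there is none to reproduce. The check is a calendar and a count, followed by an illustration.

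**1. Calendar.** The inputs are Section 10.1.1, the dosing days in Section 12.1 and the minimum 7-day washout. There is no Day 0.

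- LOXO-292 alone: from the Period 1 dose to the first Period 2 dose is 7 days at the minimum washout.
- Part 1, Period 2: Day -4 to release on Day 8 is 4 + 7 = 11 days. The last itraconazole dose is on Day 7, so follow-up is near Day 14, which is 4 + 13 = 17 days from Day -4. Counted from the LOXO-292 dose on Day 1, these are 7 and 13 days.
- Part 2, Period 2: Day 1 to release on Day 17 is 16 days. The last rifampin dose is on Day 16, so follow-up is near Day 23, which is 22 days from Day 1.

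**2. Count of timed questions for a completer.**

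| | Alone (A or C) | Coadministered (B or D) |
|---|---|---|
| While confined | 0 | 1 (release) |
| After discharge | 0 | 1 (follow-up) |

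The two questions are not equivalent. The follow-up question covers only the days after discharge, when surveillance in the unit has ended. It is the means of observing an added stretch of time, and so belongs with unequal length of observation. The release question is the clear asymmetry, because it sits on top of confined monitoring in one condition and has no counterpart in the other. It asks about present feeling and states no look-back to Period 1.

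There is one exception. A subject who leaves during Period 1 is released, and followed up, after LOXO-292 alone.

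**3. Illustration under equal true rates.** Let s be the share of events caught by continuous monitoring, and q the share of the remainder that the later questions bring out, all credited to coadministration. The recorded ratio, coadministered to alone, is

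R = [s + (1 − s)q] / s

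| s | q = 0.25 | q = 1 |
|---|---|---|
| 1.0 | 1.00 | 1.00 |
| 0.9 | (0.9 + 0.025)/0.9 = 1.03 | 1/0.9 = 1.11 |
| 0.7 | (0.7 + 0.075)/0.7 = 1.11 | 1/0.7 = 1.43 |
| 0.5 | (0.5 + 0.125)/0.5 = 1.25 | 1/0.5 = 2.00 |

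The protocol gives neither s nor q; both are assumptions.

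**4. In subjects, release question only.** Take 12 in Part 1 (3 sentinel from the Synopsis plus 9 remaining from the revision history; using 12 for Part 2 is an assumption). If the question brings out a new event in a fraction h of subjects, it adds at most 12h, or 1.2 to 3.6 for h from 0.10 to 0.30. Subjects who already have an event cannot be added again. If 30% do, the figure is 12 × 0.7 × h, or about 0.8 to 2.5. The values of h and the 30% are also assumptions.

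**The case against.** The strongest reply is that the two questions are not the surveillance system. Monitoring runs from consent onward in a confined unit, the same reporting rule covers both periods, and Section 8.3 names AE questioning without limiting it to Period 2. Untimed questioning in Period 1 is therefore not ruled out. The AE Monitoring row of the flow charts cannot be read reliably in the extracted text and settles nothing either way. Site procedures or the case report form may set question times. The AE output is descriptive, with no test or threshold. The columns already differ in the interacting drug, the period and the duration. How events are assigned to treatment is normally left to the analysis plan, so an event recalled at release with onset in Period 1 could still be credited to LOXO-292 alone.

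Most of this stands, and it limits what can be claimed. A reader might infer that Period 1 symptoms are found only if volunteered, or that the comparison is biased. The documents say neither. A reader might also count two questions against none and compute 12 × [1 − (1 − h)²], or 2.3 to 6.1 extra subjects for h from 0.10 to 0.30. That treats the follow-up question as extra elicitation in the same window, takes the two questions as independent and ignores subjects who already have an event.

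The reply does not remove the asymmetry itself. Section 13 is where procedures are described in detail, and it times a question on one side only. Nothing in the protocol makes untimed questioning equal between periods.

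**Conclusion.** The point holds as a risk of unequal elicitation. For completers, no timed question follows Treatment A or C, while the release question, and after discharge the follow-up question, come after B or D. Any resulting tilt in the by-treatment summary would tend to run against coadministration. Its size is unknown. The illustrated ratio is 1.00 if monitoring catches everything, 1.03 to 1.11 if it catches 90% and 1.11 to 1.43 if it catches 70%, all on assumed detection rates and with the extra events credited to coadministration. The documents do not support a finding of demonstrated bias. They do support a low-cost change to the questioning schedule, because the comparison serves a stated objective and the imbalance has the same direction in every completer.

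**What to change.** In Section 13.2.6.2 and the AE Monitoring row of both flow charts, schedule the same open-ended, non-leading AE question at matched PK draws that already exist after each LOXO-292 dose. For example, ask it at 24 hours after every dose, and at 168 hours after the Period 1 dose and after the last LOXO-292 dose of Period 2. Ask the Period 1 168-hour question before the first itraconazole or rifampin dose. With a 7-day washout the flow charts already place that blood draw ahead of the dose.

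Keep all treatment-emergent events in the Section 14.3.3 summary, whenever they were found, and assign them to treatment by onset time. Do not restrict the table to matched windows or move release and follow-up events to a separate listing, as that would drop genuine late events.

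The cost is protocol wording and a case report form line. Subjects are confined and already seen by staff at these draws, so no visit or procedure is added. The small downside is that a few more minor events will be recorded in Period 1.
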